### 3) Physical and Laboratory Test Findings

- a) Adequate hematologic function for participants as defined by the following:
  - i) Neutrophils  $\geq 1,500/\mu\text{L}$ .
  - ii) Platelets  $\geq 100 \times 10^3/\mu\text{L}$  (transfusion to achieve this level is not permitted within 2 weeks of first study treatment administration).
  - iii) Hemoglobin  $\geq 9 \text{ g/dL}$  (transfusion to achieve this level is not permitted within 2 weeks of first study treatment administration).
  - iv) WBC  $\geq 2000/\mu\text{L}$ .
- b) Adequate hepatic function for participants as defined by the following:
  - i) Alanine aminotransferase (ALT) and aspartate aminotransferase (AST)  $\leq 3 \times$  upper limit of normal (ULN).
  - ii) Total bilirubin  $\leq 1.5 \times$  ULN (except participants with Gilbert's syndrome who must have normal direct bilirubin).
- c) Normal thyroid function or stable on hormone supplementation per Investigator assessment.
- d) Serum creatinine  $\leq 1.5 \times$  ULN or creatinine clearance (CrCl)  $\geq 40 \text{ mL/min}$  (measured using the Cockcroft-Gault formula below):

$$\text{Female CrCl} = \frac{(140 - \text{age in years}) \times \text{weight in kg} \times 0.85}{72 \times \text{serum creatinine in mg/dL}}$$

$$\text{Male CrCl} = \frac{(140 - \text{age in years}) \times \text{weight in kg} \times 1.00}{72 \times \text{serum creatinine in mg/dL}}$$

- e) Ability to comply with treatment, PK and pharmacodynamic sample collection, and required study follow-up periods.

### 4) Age and Reproductive Status

- a) Males and females, aged at least 18 years old.
- b) Women of childbearing potential (WOCBP) must have a negative serum or urine pregnancy test (minimum sensitivity 25 IU/L or equivalent units of hCG) within 24 hours prior to the start of study treatment.
- c) Women must not be breastfeeding.
- d) WOCBP who are continuously not heterosexually active are also exempt from contraceptive requirements but should still undergo pregnancy testing as described in this section.
- e) WOCBP must agree to follow instructions for method(s) of contraception ([Appendix 4](#)) for the duration of BMS-986288 combination therapy treatment, plus 5 months post treatment completion. WOCBP receiving monotherapy treatment with BMS-986288 must agree to follow instructions for method(s) of contraception for the duration of monotherapy treatment with BMS-986288, plus 3 months post treatment completion. Local laws and regulations may require use of alternative and/or additional contraception methods. See [Appendix 4](#).

- f) **Not Applicable as of Amendment 02:** Males who are sexually active with WOCBP must agree to follow instructions for method(s) of contraception and fetal protection (Appendix 4) for the duration of BMS-986288 combination treatment, plus 5 half-lives of nivolumab, plus 90 days (duration of sperm turnover), for a total of 215 days post treatment completion. Males who are sexually active with WOCBP must agree to follow instructions for methods of contraception during monotherapy treatment with BMS-986288, plus 5 half-lives of BMS-986288, plus 90 days (duration of sperm turnover), for a total of 165 days post treatment completion. In addition, male participants must be willing to refrain from sperm donation during this time. See Appendix 4.
- g) WOCBP who are continuously not heterosexually active are exempt from contraceptive requirements, and still must undergo pregnancy testing as described in this section.
- h) WOCBP must agree to follow instructions for method(s) of contraception (Appendix 4) for the duration of treatment, plus 2 months after last dose of regorafenib (or local guidelines). Local laws and regulations may require use of alternative and/or additional contraception methods. See Appendix 4.

Investigators shall counsel WOCBP on the importance of pregnancy prevention and the implications of an unexpected pregnancy. Investigators shall advise on the use of highly effective methods of contraception (Appendix 4), which have a failure rate of < 1% when used consistently and correctly.

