### **9.2.5 Pregnancy**

If, following initiation of the study treatment, it is subsequently discovered that a participant is pregnant or may have been pregnant at the time of study exposure, including █ months after BMS-986288 combination therapy, █ months after BMS-986288 monotherapy administration, and 2 months after the last dose of regorafenib, the Investigator must immediately notify the BMS Medical Monitor/designee of this event and complete and forward a Pregnancy Surveillance Form to BMS Designee within 24 hours of awareness of the event and in accordance with SAE reporting procedures described in [Appendix 3](#).

In most cases, the study treatment will be permanently discontinued in an appropriate manner. Please call the BMS Medical Monitor (or designee) within 24 hours of awareness of the pregnancy. Protocol-required procedures for study discontinuation and follow-up must be performed on the participant.

If, for whatever reason, the pregnancy has ended, confirmed by negative serum pregnancy test, treatment may be resumed (at least 3 weeks after the pregnancy has ended), following approvals of participant/sponsor/IRB/EC, as applicable.

Follow-up information regarding the course of the pregnancy, including perinatal and neonatal outcome and, where applicable, offspring information must be reported on the Pregnancy Surveillance Form.

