#### **End of Relevant Systemic Exposure**

End of relevant systemic exposure is the timepoint where the Investigational Medicinal Product (IMP) or any active major metabolites have decreased to a concentration that is no longer

considered to be relevant for human teratogenicity or fetotoxicity. This should be evaluated in context of safety margins from the no-observed-adverse-effect level or the time required for 5 half-lives of the IMP to pass.

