## **CONTRACEPTION GUIDANCE FOR FEMALE PARTICIPANTS OF CHILD BEARING POTENTIAL**

One of the highly effective methods of contraception listed below is required during study duration and until the end of relevant systemic exposure. For combination therapy with BMS-986288 plus nivolumab, relevant systemic exposure is defined as 125 days after the end of study treatment, plus 30 days, for a total of 155 days post treatment completion. For monotherapy with BMS-986288, relevant systemic exposure is defined as 75 days after the end of study treatment, plus 30 days, for a total of 105 days post treatment completion.

Local laws and regulations may require use of alternative and/or additional contraception methods.

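### Criterion 4e sets 3 months of contraception after BMS-986288 monotherapy, 13 to 16 days short of the 105 days that Appendix 4 requires (minor)

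*Combined protocol and SAP*

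**What the plan says.** Section 6.1, item 4 (Age and Reproductive Status), criterion e, sets the commitment that a woman of childbearing potential makes at entry. On BMS-986288 monotherapy she agrees to contraception during treatment "plus 3 months post treatment completion". The criterion ends by referring the reader to Appendix 4.

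Appendix 4 (contraception guidance for female participants) states that a highly effective method "is required during study duration and until the end of relevant systemic exposure". For monotherapy, "relevant systemic exposure is defined as 75 days after the end of study treatment, plus 30 days". The appendix gives the sum as 105 days, again counted from when treatment is completed.

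The same appendix explains how the end of relevant systemic exposure should be judged: from safety margins, or by "the time required for 5 half-lives of the IMP to pass".

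Section 9.2.5 sets a pregnancy-notification window that includes a number of "months after BMS-986288 monotherapy administration". That number is redacted in the public copy, so the section supports neither figure.

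**The concern.** Both texts are current, both apply to the same women on the same drug, and both count from the end of treatment. They give different durations, and no sentence says which one governs.

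The eligibility criterion is the one a site is likely to counsel from, and it carries the shorter period. A woman who was told 3 months and kept to it would satisfy criterion 4e and still fall short of Appendix 4. At stake is a fetal-exposure precaution for an investigational anti-CTLA-4 antibody. No efficacy or safety analysis depends on it.

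**Working it through.** **Inputs**

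- Criterion 4e, monotherapy: 3 months after treatment.
- Appendix 4, monotherapy: 75 days plus 30 days.
- For comparison, combination therapy: 5 months in criterion 4e; 125 days plus 30 days in Appendix 4.
- Cross-check on the 75 days: criterion 4f, the male contraception rule, which has not applied since Amendment 02. It reads "plus 5 half-lives of BMS-986288, plus 90 days (duration of sperm turnover), for a total of 165 days post treatment completion".

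**Step 1. Reproduce the Appendix 4 total.** 75 + 30 = 105 days, as stated.

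**Step 2. Convert 3 months to days.** Three calendar months were counted from each of the 1,461 dates in a four-year run that starts on 1 January 2023 and includes a leap year. The span is 92 days for 845 dates, 91 for 313, 90 for 216 and 89 for 87. The range is therefore 89 to 92 days.

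**Step 3. Find the shortfall.**

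- Smallest: 105 − 92 = 13 days.
- Largest: 105 − 89 = 16 days.

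**Step 4. Locate the shortfall.** Criterion 4e runs past the 75-day mark by 89 − 75 = 14 to 92 − 75 = 17 days. The uncovered days start at day 90 to 93 and end at day 105, so they all lie within the 30-day add-on (days 76 to 105). The share of the add-on lost is 13/30 = 43% to 16/30 = 53%.

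**Step 5. Check what the 75 days represents.** From criterion 4f, 165 − 90 = 75 days for 5 half-lives of BMS-986288. This agrees with the 5-half-life basis that Appendix 4 allows. Because 4f is superseded, it serves only as corroboration. The protocol gives no reason for the further 30 days.

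**Step 6. Test the rounding explanation.** At 30.4375 days per month:

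| Regimen | Appendix 4 total | In months | Criterion 4e | 4e in days | Gap |
|---|---|---|---|---|---|
| Monotherapy | 105 days | 105 / 30.4375 = 3.45 | 3 months | 89–92 | 13–16 days |
| Combination | 155 days | 155 / 30.4375 = 5.09 | 5 months | 150–153 | 2–5 days |

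Rounding to the nearest whole month would produce both figures in criterion 4e. For the combination it costs a few days; for monotherapy it costs about two weeks.

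**The case against.** The strongest reply is that criterion 4e does not stand alone. It refers to Appendix 4, and the text that closes the reproductive-status criteria sends investigators there again. Appendix 4 is the only place with a derivation, and applying 105 days satisfies both texts, so no site has to breach one to obey the other. This stands in part. However, the monotherapy sentence has only the general reference at the end of the criterion, and that reference does not say which duration prevails.

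Second, the figure looks like a rounded month count, produced by the same convention as the combination figure. That is plausible. But rounding a protective minimum downward still leaves the criterion below the total that the appendix requires.

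Third, there is a safeguard. Table 2-3 schedules pregnancy tests at 30, 60 and 100 days (± 7), counted from the last dose or discontinuation, whichever is later. The third test falls at days 93 to 107, in or close to the disputed period. It would detect a pregnancy but not prevent one.

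Fourth, what participants are actually told depends on the consent form, which is not available for this review, and the Section 9.2.5 figure is redacted. This is a fair limit: early stopping is possible, not established.

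Finally, 3 months covers the whole 75-day component, and only monotherapy participants are concerned. Both points stand, and they hold the severity at minor.

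**Conclusion.** The inconsistency holds as stated, at minor severity. Criterion 4e is 13 to 16 days shorter than the monotherapy period in Appendix 4, and the protocol does not say which applies.

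The practical risk is small. The missing days fall wholly within the 30-day add-on, and 3 months runs 14 to 17 days beyond the 75-day component. No endpoint, sample size or analysis changes. The number of women affected cannot be judged, because the documents do not give it.

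The size rests on reading 3 months as calendar months and on both periods starting at treatment completion, as both texts say. The combination difference of 2 to 5 days is treated as rounding, and the regorafenib period agrees between criterion 4h and Section 9.2.5. Neither is part of this point, and no inconsistency is claimed for the redacted monotherapy window in Section 9.2.5.

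**What to change.** State one monotherapy period in both places. The simplest change is to replace 3 months with 105 days in criterion 4e: it is the only figure with a stated derivation, and observing it already satisfies both texts. If the sponsor holds that 3 months is correct, the Appendix 4 total should be amended instead.

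Then confirm that the consent form and the monotherapy window in Section 9.2.5 carry the same period.

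The cost is one figure changed and two checks. Nothing needs to change for combination therapy or regorafenib.

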## 6.2 Exclusion Criteria

### 1) Target Disease Exclusions

- a) Participants with primary CNS malignancies, tumors with CNS metastases as the only site of disease, [REDACTED] brain metastases, or leptomeningeal metastasis will be excluded. However, participants with [REDACTED] metastases are eligible. [REDACTED] following radiation and/or surgical treatment (or 4 weeks of observation if no intervention is clinically indicated), and no longer taking steroids for at least 2 weeks prior to first dose of study treatment, and with no new or progressive neurological signs and symptoms.

- b) For Part 2C:

- i) Participants with [REDACTED] mutant [REDACTED].
    - (1) Verify [REDACTED] status based on available local testing results as part of medical history prior to study treatment. [REDACTED]

### 2) Prohibited Treatments

- a) Cytotoxic agents, unless at least 4 weeks have elapsed from last dose of prior anti-cancer therapy and initiation of study therapy.
- b) Noncytotoxic agents, unless at least 4 weeks or 5 half-lives (whichever is shorter) have elapsed from the last dose of prior anti-cancer therapy and the initiation of study therapy. If 5 half-lives is shorter than 4 weeks, agreement with the Sponsor/Medical Monitor (or designee) is mandatory.

- c) Prior immunotherapy treatments, unless at least 4 weeks or 5 half-lives (whichever is shorter) have elapsed from the last dose of immune therapy and initiation of study therapy. See [Section 6.1](#) for additional requirements for prior immunotherapy treatments.
- d) Any botanical preparation (eg, herbal supplements or traditional Chinese medicines) intended to treat the disease under study within 4 weeks prior to treatment. If less than 4 weeks have elapsed from the last botanical supplement and the initiation of study treatment, the participant can be treated at the Investigator's discretion and in agreement with the Sponsor/Medical Monitor (or designee).
  - i) Use of marijuana and its derivatives for treatment of symptoms related to cancer or cancer treatment are permitted if obtained by medical prescription or if its use (even without a medical prescription) has been legalized locally.
- e) Participants who have received live/attenuated vaccine within 30 days of first treatment.
  - i) The use of inactivated seasonal influenza vaccines (eg, Fluzone®) will be permitted on study without restriction.
- f) Previous SARS-CoV-2 vaccine within 7 days of Cycle 1 Day 1 (C1D1). For vaccines requiring more than 1 dose, the full series (eg, both doses of a 2-dose series) should be completed prior to enrollment when feasible and when a delay in enrollment would not put the study participant at risk.
- g) Treatment with complementary medications (eg, herbal supplements or traditional Chinese medicines) to treat the disease under study within 2 weeks prior to first study treatment. Such medications are permitted if they are used as supportive care. Refer to [Section 7.7.1](#) for prohibited therapies.
- h) Concomitant participation in treatment period of any clinical vaccine studies.
- i) Prior radiotherapy must be completed at least 2 weeks prior to treatment allocation. Participants must have recovered from all radiation-related toxicities.
- j) For Part 2C:
  - i) Prior treatment with an [REDACTED] antibody.  
[REDACTED]

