**Table 2-1: Screening Schedule of Activities for All Study Parts**

Procedure	Screening Visit (Days -30 to -1)	Notes
Laboratory Tests	X	See Clinical Laboratory Assessments in Section 9.4.5 and Table 9.4.5-1 .
Urinalysis	X	Microscopic urine reflex only for urinalysis positive for blood/protein/leukocytes.
Serology	X	Includes hepatitis C Ab, hepatitis B surface antigen, and HIV-1 and HIV-2 antibody (see Section 9.4.5 and Table 9.4.5-1).
Pregnancy Test	X	For WOCBP only. Serum to be collected at screening and within 24 hours prior to dosing. Serum pregnancy test may be taken on the first day of treatment, provided results are available prior to starting study therapy. If pregnancy test is taken within 24 hours of dosing (C1D1), a further pregnancy test is not required.
FSH	X	Women only, as needed to document postmenopausal status. Females under the age of 55 years must have a serum FSH level > 40 mIU/mL to confirm menopause.
Adverse Event Reporting		
Assessment of Signs/Symptoms/ Clinical Complaints	X	
Monitor for SAEs	X	All SAEs must be collected from the date of participant's written consent until 100 days after discontinuation of dosing. All AEs (SAEs or nonserious AEs) associated with SARS-CoV-2 infection collected from time of consent.
Tumor Assessments		
Body Imaging	X	Contrast-enhanced CT of the chest, abdomen, pelvis, and all other known and/or suspected sites of disease, within 30 days prior to first dose. For participants with cancer of the head and neck, a CT or MRI of the neck is required. For participants with TNBC without measurable lesions outside of the breast, contrast-enhanced MRI of the breasts should be performed. See Section 9.1.1 for further details.

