(1) Microsatellite status should be performed per local standard of practice, IHC and/or PCR. If the MSI molecular test and MMR IHC test results are both available, then both MSS and MMR proficiency will be required for study entry. Patients with MSI-high or MSI-low or MMR deficiency will not be eligible.

(2) KRAS and NRAS (extended RAS) and [REDACTED] status should be verified based on available local testing results as part of medical history. Regardless of whether or not RAS mutation status is known, all participants will be tested during screening for extended RAS (NRAS and KRAS) and BRAF mutation status. Results from this testing at screening is not required prior to receiving treatment on study (except [REDACTED]). Note: If results are not known, then a sample [REDACTED] should be sent for testing locally. [REDACTED] may be used if [REDACTED] results are not feasible, with prior Sponsor approval. The proportion of participants with [REDACTED] will be monitored on an ongoing basis. The sponsor may limit the number of [REDACTED] participants after discussion with the investigators. Patients with [REDACTED] are not eligible for the study.

(3) Participants with 3L/4L mCRC must have progressed or been intolerant to 2 prior lines of chemotherapy in the metastatic disease setting, which must include at least oxaliplatin- and irinotecan-containing regimens.

(a) Participants who received FOLFOXIRI (or equivalent) in the 1L setting may be considered for enrollment in the second line setting.

(b) Prior therapies containing anti-VEGF agents and/or anti-EGFR agents are permitted.

(c) Disease recurrence within 6 months after the last dose of the adjuvant/neoadjuvant therapy is permitted and will be considered as 1 line of prior therapy for study entry. Disease recurrence beyond 6 months after the last dose of the adjuvant/neoadjuvant therapy is also permitted but will NOT be considered as 1 line of prior therapy for study entry.

(d) Disease progression must have occurred during or within 3 months following the last dose of approved standard therapies

(4) Participants must have measurable disease per RECIST 1.1 ([Appendix 5](#)). Participants with lesions in a previously irradiated field as the sole site of measurable disease will be permitted to enroll provided the lesion(s) have demonstrated clear progression and can be measured accurately.

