### **7.7.3 Palliative Local Therapy**

Palliative and supportive care for disease-related symptoms may be offered to all participants on the study. Limited radiation treatment or surgery to control isolated lesions may be permitted for participants following consultation with the BMS Medical Monitor (or designee).

Participants should not receive study treatment during radiation because the potential for overlapping toxicities with radiotherapy and study treatment is not known. If palliative radiotherapy in short courses and for isolated fields is required to control symptoms not clearly related to disease progression, then study treatment administration should be withheld, if possible, for at least 1 week before radiation and for at least 1 week after its completion.

Participants should be closely monitored for any potential toxicity during and after receiving radiotherapy. Prior to resuming study treatment, radiotherapy-related AEs should resolve to Grade  $\leq$  1 or baseline, and participants must meet relevant eligibility criteria as determined by the BMS Medical Monitor (or designee) in discussion with the investigator. The BMS Medical Monitor (or designee) must be consulted prior to re-initiating study treatment in a participant with a dosing delay lasting  $>$  8 weeks from the previous dose.

Details of palliative radiotherapy should be documented in the source records and electronic case report form (eCRF). Details in the source records should include dates of treatment, anatomic site, dose administered and fractionation schedule, and AEs. Symptoms requiring palliative radiotherapy should be evaluated for objective evidence of disease progression. If a participant is considered to have progressed at the time of palliative therapy, then they must meet the treatment beyond progression criteria ([Section 5.1.4](#)) prior to re-initiating study treatment. Participants receiving palliative radiation of target lesions will have the evaluation of ORR just prior to radiotherapy, but these participants will no longer be evaluable for the determination of response subsequent to the date palliative radiation occurs.

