## 1.4 Baseline Documentation Of 'Target' And 'Non-Target' Lesions

When more than one measurable lesion is present at baseline all lesions up to a maximum of five lesions total (and a maximum of two lesions per organ) representative of all involved organs should be identified as target lesions and will be recorded and measured at baseline (this means in instances where patients have only one or two organ sites involved a maximum of two and four lesions respectively will be recorded).

Note: A maximum of two lesions can be selected per organ system. For example, a maximum of two lung lesions can be selected (selected from one lung or one lesion from each). A maximum of two lymph nodes can be selected at baseline, as the lymphatic system is considered one organ.

Target lesions should be selected on the basis of their size (lesions with the longest diameter), be representative of all involved organs, but in addition should be those that lend themselves to reproducible repeated measurements. It may be the case that, on occasion, the largest lesion does not lend itself to reproducible measurement in which circumstance the next largest lesion which can be measured reproducibly should be selected.

A sum of the diameters (longest for non-nodal lesions, short axis for nodal lesions) for all target lesions will be calculated and reported as the baseline sum diameters. If lymph nodes are to be included in the sum, then as noted above, only the short axis is added into the sum. The baseline sum diameters will be used as reference to further characterize any objective tumor regression in the measurable dimension of the disease.

All other lesions (or sites of disease) including pathological lymph nodes should be identified as non-target lesions and should also be recorded at baseline. Measurements are not required and these lesions should be followed as 'present', 'absent', or in rare cases 'unequivocal progression' (more details to follow). In addition, it is possible to record multiple non-target lesions involving the same organ as a single item on the case record form (eg, 'multiple enlarged pelvic lymph nodes' or 'multiple liver metastases').

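### Radiotherapy may end after, or shortly before, the baseline scan and no general rule keeps irradiated lesions out of the target set, so radiation shrinkage can be scored as response

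*Combined protocol and SAP*

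**What the plan says.** Section 6.2, Prohibited Treatments, item i), sets the washout for all parts: "Prior radiotherapy must be completed at least 2 weeks prior to treatment allocation". The Body Imaging row of Table 2-1 covers "all other known and/or suspected sites of disease, within 30 days prior to first dose". Neither place requires the scan to follow the radiotherapy.

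Appendix 5 defines measurability by size (Section 1.1). On choosing targets, Section 1.4 says: "Target lesions should be selected on the basis of their size (lesions with the longest diameter". It adds that targets should represent the involved organs and be measurable reproducibly. It does not mention irradiated or locally treated lesions. Partial response is a fall of at least 30% from the baseline sum (Section 2.1). ORR counts every treated participant whose best response is CR or PR (Table 10.3.1-1), and Section 9.1.1.2 requires confirmation at least 4 weeks later.

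Two places do deal with irradiated lesions:

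- **Part 2C criterion (4), Section 6.1:** "Participants with lesions in a previously irradiated field as the sole site of measurable disease will be permitted to enroll". The condition attached is that such a lesion has clearly progressed and allows accurate measurement.
- **Section 7.7.3, radiation during the study:** "Participants receiving palliative radiation of target lesions will have the evaluation of ORR just prior to radiotherapy". After that the participant is no longer evaluable for response.

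**The concern.** A lesion irradiated shortly before study drug may go on shrinking without any drug effect. If it was measured before or soon after the radiation and chosen as a target, the later fall is credited to study treatment. Confirmation 4 weeks later does not separate the two causes, because a lesion shrunk by radiation can still be small at the second scan.

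The protocol already accepts the principle. Section 7.7.3 stops response evaluation when a target is irradiated on study, and Part 2C asks for progression of an irradiated sole-site lesion. Neither rule reaches an irradiated lesion that sits beside another measurable lesion in Part 2C, or any irradiated lesion in Parts 1, 2A and 2B. Such lesions are foreseen: Section 6.1 admits Part 2C participants after local liver treatment, including selective internal radiation.

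At stake is ORR. It sizes Parts 2A and 2B (Sections 10.1.4 and 10.1.5) and is the primary endpoint of Part 2C.

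**Working it through.** **Plan's own figure.** The nearest is the power for ORR in Part 2C: about 80% at two-sided alpha 0.1, or about 73% without borrowed controls (Section 10.1.6). Arm sizes and the ORR difference are blacked out, so it cannot be reproduced. The point does not dispute it.

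**1. Overlap of the windows.** Inputs: scan up to 30 days before first dose (Table 2-1); radiotherapy ending at least 14 days before allocation (Section 6.2). The gap g from allocation to first dose is not given, so it is ranged.

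Days on which radiotherapy can end after the scan = max(0, 30 − 14 − g)

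| g (days) | 0 | 3 | 7 | 14 | 16 or more |
|---|---|---|---|---|---|
| Overlap (days) | 16 | 13 | 9 | 2 | 0 |

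For curative radiotherapy in Part 1 head and neck cancer, Section 6.1 sets 4 weeks before first study drug, so the overlap there is 30 − 28 = 2 days.

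**2. Shrinkage needed for one irradiated lesion to give a PR alone.** If it carries a share w of the baseline sum and the rest is unchanged, it must shrink by 0.30 / w.

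- Only target (w = 1): 30%.
- One of two equal targets: 60%.
- One of three: 90%.
- One of four or five: 120% or 150%, which is impossible.

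Example: targets of 40 mm and 20 mm, sum 60 mm. If the 40 mm lesion halves, the sum is 40 mm, a change of −20/60 = −33%: PR. If the other lesion meanwhile grows from 20 to 23 mm, the sum is 43 mm, a change of −17/60 = −28%: no PR.

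**3. Single-arm illustration.** Section 10.1.5 tests Part 2B at one-sided 0.10 against a null ORR, but n and the null rate are blacked out. All values here are assumed. The bar r is the smallest number of responders with P(X ≥ r | n, null) ≤ 0.10. For n = 40 and null 10%, P(X ≥ 6) = 0.206 and P(X ≥ 7) = 0.100, so r = 7. The false-positive rate is P(X ≥ r) at the null plus the added points.

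| Assumed design | No rise | +1 point | +2 points | +3 points |
|---|---|---|---|---|
| n=40, null 10%, bar 7 | 0.100 | 0.14 | 0.198 | 0.259 |
| n=30, null 10%, bar 6 | 0.073 | 0.105 | 0.143 | 0.187 |
| n=40, null 5%, bar 5 | 0.048 | 0.090 | 0.145 | 0.213 |

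For scale: if 10% of participants had such a target and 20% to 30% of those reached a 30% fall, ORR would rise by 2 to 3 points (0.10 × 0.20 to 0.10 × 0.30). Both inputs are assumptions.

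**4. Randomized illustration (Part 2C).** Assume 80 versus 40 participants (the 2:1 ratio of Section 7.2) and ORR 15% versus 2%. If a fraction f of non-responders in each arm becomes a radiation-only responder, each rate p becomes p + (1 − p)f, and the difference becomes 0.13 × (1 − f).

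| f | Difference | Power (two-sided 0.1) |
|---|---|---|
| 0 | 13.0 points | 0.76 |
| 2% | 12.7 points | 0.67 |
| 5% | 12.4 points | 0.56 |

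The difference shrinks and power falls. The experimental arm is not favoured.

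**The case against.** The documents show a possibility, not an event. A participant must have had recent radiotherapy to a lesion that was chosen as a target and carries enough of the sum, with no offsetting growth, no new lesion, no non-target progression, and confirmation. The documents do not say how often that happens. All of this stands, and it is why the size is left open.

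Section 7.7.3 might already cover part of the gap. A participant counts as enrolled from consent (Table 2-1), and screening is one of the study periods (Section 5.1). Palliative radiation of a target between consent and first dose could then fall under it. But that section is written mainly around interrupting and resuming study treatment, and Section 9 lets scans made before consent serve as baseline. The reading is arguable and incomplete.

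Appendix 5 adapts a published guideline, and an Imaging Manual exists. Either might hold a rule. Neither is available here, and Section 9.1.1.2 points to Appendix 5 for the criteria to be used, so the rule belongs there.

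Screening records prior local therapy, so affected participants could be found for a sensitivity analysis. Locally treated liver metastases count as liver metastases in the Part 2C stratification (Section 5.4.4), which helps balance the randomized arms. Both points reduce the harm; neither changes how response is scored.

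For Part 2A, Section 10.1.4 gives only confidence limits at assumed ORR estimates and no null rate, so no false-positive rate is defined there. In Parts 2A and 2B ORR is a secondary endpoint, and the initial look in Part 2B is descriptive. These points stand.

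**Conclusion.** The gap is real. Followed as written, the plan can score radiation shrinkage as response, which Section 7.7.3 and Part 2C criterion (4) indicate the sponsor does not want.

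- **Parts 1, 2A and 2B:** the uncontrolled ORR can be inflated. Only Part 2B states a test against a null ORR. Under the assumed n=40, null 10% and bar of 7, 1 to 3 extra points take the false-positive rate from 0.10 to between 0.14 and 0.26.
- **Part 2C:** the expected effect within the randomized comparison is dilution and lost power. Bias arises only if borrowed control data handled such lesions differently. Section 5.4.8 says eligibility matches the control trial but does not address this.

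A reader might infer that ORR is inflated in this trial, that 16 days is the usual overlap, or that Part 2C is biased towards the combination. The documents support none of these. The frequency of recent radiotherapy is not given, 16 days requires allocation on the day of first dose, and both randomized arms follow the same rules. This is a worthwhile, cheap improvement of unknown size.

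**What to change.** In Appendix 5 Section 1.4, for all parts and for both investigator and BICR reads, state that:

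1. a lesion irradiated or otherwise locally treated before first dose may be a target only if imaging shows progression of that lesion after that treatment;
2. otherwise it is recorded as non-target;
3. a lesion irradiated after the baseline scan is never a target.

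Align Part 2C criterion (4) by saying that the progression must follow the radiotherapy and by removing the sole-site limit. Leave the radiotherapy washout, and eligibility outside Part 2C, unchanged.

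Requiring only that the baseline scan follow radiotherapy would bring the overlap to 0 days, but delayed shrinkage of a freshly irradiated lesion would still count. The rule on target selection is therefore needed.

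Cost: a short text change and a matching line in the Imaging Manual, with no new on-study scans. Existing scans from before baseline must reach the investigator and the central reader so that progression can be shown. Some participants lose a target lesion. A few may have none; they would be read with the Appendix 5 table for non-target disease only and stay in the all-treated denominator.
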